14.3 Vital signs

The summary of vital signs will only include on treatment data, which are defined as those vital sign measurements after the first dose of study treatment and on or before last dose + 84 days.

Analysis in vital sign measurement using descriptive summary statistics for the change from baseline for each post-baseline visit in extension only be presented for subjects with both a baseline (of core study) and post baseline values. These descriptive summaries will be presented by vital sign and treatment dose. Change from baseline will only be summarized for subjects with both baseline and post-baseline values and will be calculated as:

$$\text{change from baseline} = \text{post-baseline value} - \text{baseline value}$$

Analysis in vital sign measurements using descriptive summary statistics for the change from baseline until each post-baseline visit will be performed.

The number and percentage of subjects with newly occurring notable vital signs will be presented. Criteria for notable vital sign abnormalities are provided in [Table 13-4](#) below.

Table 14-4 Criteria for notable vital sign abnormalities

Vital sign (unit)	Notable abnormalities
Systolic blood pressure (mmHg)	>= 140 mmHg or < 90 mmHg
Diastolic blood pressure (mmHg)	>=90 mmHg or <60 mmHg
Pulse (bpm)	> 100 bpm or <60 bpm

Individual subject listing of vital signs and a listing for the newly occurring notably abnormalities will be provided.

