12.4 Analysis of Primary Variable(s)

The primary efficacy variable(s) is the clinical response to treatment according to ACR20, ACR50 and ACR 70 improvement in disease activity over time up to Week 260.

ACR response criteria denote the response (i.e., improvement) in signs & symptoms of the disease of a subject compared to baseline of the core study.

The analysis of the primary variables will be based on the FAS. Primarily, CRP will be used instead of ESR to calculate ACR response; ESR will only be used in the event CRP is missing.

Shift tables will be provided comparing the subject's ACR evaluation at the pre up-titration visit relative to the observed data of the following week intervals after up-titration: (12-32 weeks), (36-56 weeks) and (60-80 weeks). The ACR grouping presented in the table will be: $ACR < 20$, $20 \leq ACR < 50$, $50 \leq ACR < 70$, $ACR \geq 70$.

Graphical representation (line plots) of ACR20, ACR50 and ACR70 response over time and Sankey-style bar chart for the ACR response within the subjects that up-titrated from 150 mg to 300 mg (provided that up-titration has been occurred for more than 8 weeks) will be drawn from the observed data.

Additionally, observed data tables will summarize the ACR20, ACR50 and ACR70 response following up-titration when assessed. Results will be illustrated in line plots.

Also individual subject listings of the ACR components as well as for the ACR20/50/70 response will be given.

Statistical model, hypothesis, and method of analysis

No formal hypotheses are planned for this study. The proportion of subjects meeting the ACR criteria (ACR20, ACR50, and ACR70) will be descriptively summarized for each treatment by absolute and relative frequencies followed by 95% confidence intervals for the proportion of patients responding to treatment according to the ACR criteria from Week 1 onwards based on the pooled data from core and extension study. Results regarding ACR20/50/70, will be presented overall in the FAS population as well as in subgroups by TNF α status (naive or IR) and by concomitant use of MTX as appropriately.

Placebo group (core study) in efficacy analysis will not be considered.

All the above efficacy variables will be analyzed on the FAS (unless otherwise specified) for all applicable analysis visits based on the observed data.

For binary variables, the proportion of responders along with the 95% CI will be presented by treatment groups over analysis visits.

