13.1 Pharmacokinetics

All completed subjects with quantifiable pharmacokinetic (PK) measurements of secukinumab will be included in the pharmacokinetic data analysis. Serum concentrations will be expressed in mass per volume units. All concentrations below the limit of quantification as well as missing data will be labeled as such in the concentration data listings. PK concentrations will be summarized by visit and treatment group. In addition to mean, standard deviation (SD), coefficient of variation (CV), median and quartiles, the geometric mean and geometric coefficient of variation (CV) and n(log) will be presented. The formula for deriving the geometric mean and CV (%) is as following:

- $CV (\%) = (SD/mean) * 100$,
- $geometric\ mean = \exp(\text{sum of log transformed data} / \text{number of non-missing data points after log transformation})$,
- $geometric\ CV = \sqrt{\exp(\text{variance of log-transformed data}) - 1} * 100$.

In addition, sample number, concentration, sample date, sample time at pre-dose and minutes pre-dose will be listed by treatment sequence.

Values below lower limit of quantification/below detection limit will be imputed by 0.

Pharmacokinetic data of the study treatment will be analyzed with a population-pharmacokinetic mixed effects model. The analysis will be based on a pooled data set, including pharmacokinetic samples from previous studies. The modeling approach will be further detailed in a modeling plan. Results will be reported separately.

14 Safety evaluation

Safety analyses will be done on the safety set.

Summaries will be presented cumulatively from core and extension. For subjects who switched from placebo to secukinumab in core, their data prior to switch will only be reported in in-text tables and listings.

Safety analyses will be performed on treatment received or actual treatment as described below:

The actual treatment or treatment received for summaries of safety data will differ to the treatment assigned at randomization if a subject received the wrong treatment during the core and extension study or if the subject up-titrated to a higher dose.

Subjects who switch treatment during the study (e.g. from placebo to active treatment, or had dose escalation) will be counted to both groups using the appropriate start and stop exposure date.

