14.1 Adverse events

The crude incidence of treatment emergent adverse events on secukinumab (i.e. events started after the first dose of secukinumab in core study or events present prior to the first dose of secukinumab but increased in severity based on preferred term and within 84 days after last dose of secukinumab) will be summarized by primary system organ class and preferred term for the entire treatment period. Confidence intervals for the crude rate will be derived as described in Section 17.2.3.1 In addition, exposure time-adjusted rates (incidence rate) including 95% confidence intervals will be provided for selected terms for the entire treatment period, (see Section 17.2.4.1) to adjust for differences in exposure.

Adverse events reported will be presented in descending frequency according to its incidence in total secukinumab group (combining all secukinumab treatment groups) starting from the most common event.

Summary statistics will be provided by primary system organ class and preferred term for the entire treatment period for all TEAEs, for serious TEAEs, for possibly related TEAEs, for deaths, for TEAEs causing treatment discontinuation, other serious or clinically significant treatment emergent adverse events or related discontinuations, for TEAEs leading to temporary dose interruptions, for SPP risks and for adjudicated major adverse cardiovascular events (MACE). Separate summaries for adverse events suspected to be related to study drug, will also not be displayed in the current analysis.

TEAEs will also be summarized by primary system organ class and preferred term for the entire treatment period in time segments of 52 and 26 weeks.

Summaries (crude incidence only) will be presented for TEAEs by maximum severity as well. If a particular AE 'severity' is missing, this variable will be listed as missing and treated as missing in summaries.

If a subject reported more than one adverse event with the same preferred term, the adverse event with the greatest severity will be presented. If a subject reported more than one adverse event within the same primary system organ class, the subject will be counted only once with the greatest severity at the system organ class level, where applicable.

When adjudication is required of major cardiovascular events, a summary of those types of events as reported by the investigator and confirmed by adjudication will be provided.

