Exposure adjusted incidence rates for TEAEs, selected lower lever risk terms based on TEAEs, serious adverse events, adverse events leading to discontinuation, common AEs (frequency >2% in the Any AIN457 group during the first 24 weeks of treatment or IR > 5/100 subject years during the entire treatment period), SPP risks and MACE will be summarized by primary system organ class and/or by preferred term for the entire period.

The incidence of AEs will be presented per 100 subject years of exposure.

Exposure adjusted incidence rates for TEAEs will also be provided for specific common or very common TEAEs (very common TEAEs are described in the Core Data Sheet).

Adverse events will be reported separately by SMQ according to MedDRA. The MedDRA version used for reporting will be described in a footnote.

Algorithms for date imputations will be provided in the PDS.

The safety analyses that will be performed for treatment emergent AEs, labs, ECG and vital signs for each analysis period is described in table below.

Listings will be provided for all adverse events, all non-fatal serious adverse events, deaths, adverse events leading to discontinuation from study treatment or temporary dose interruption, adverse events by SPP risks and adjudicated MACE events (myocardial infarctions, strokes, and cardiovascular deaths).

For SAEs that occurred during screening a listing will be prepared for all subjects screened including screening failures.

No graphical displays of the crude incidence rates and exposure-adjusted rates will be presented for any AEs and serious AEs by system organ class in the current interim analysis.

An overview of the safety analyses and which will be performed for each analysis period is described in [Table 14-1](#).

Table 14-1 Overview of analyses on some safety endpoints

Analysis period	AEs & SAEs	AEs by severity	Study drug related AEs	AEs-SMQ	Risk	Notables for (vitals/ ECG), lab criteria
Entire Treatment	
 •crude incidence •exposure time adjusted incidence* 	
 •crude incidence 	
 •crude incidence 	
 •exposure time adjusted incidence 	
 •crude incidence •exposure time adjusted incidence 	
 •crude incidence

*Exposure-adjusted incidence rates will be done for the following:

- at the PSOC for AE and SAE

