Summaries for newly occurring or worsening clinically notable lipid abnormalities will also be provided cumulatively for each of the following parameters and categories:

- HDL:
 - ≤LLN
 - <0.8 x LLN
- LDL, cholesterol, triglycerides:
 - ≥ULN
 - >1.5 x ULN
 - >2.5 x ULN

Newly occurring or worsening liver enzyme abnormalities will also be summarized based on the event criteria given in [Table 14-3](#):

Table 14-3 Liver-related events

Parameter	Criterion
ALT	>3xULN; >5xULN; >8xULN; >10xULN, >20xULN
AST	>3xULN; >5xULN; >8xULN >10xULN; >20xULN
ALT or AST	>3xULN; >5xULN; >8xULN >10xULN; >20xULN
TBL	>1.5xULN, >2xULN, >3xULN,
ALP	>2xULN, >3xULN. >5xULN
ALT or AST & TBL	ALT or AST >3xULN & TBL >2xULN; ALT or AST >5xULN & TBL >2xULN; ALT or AST >8xULN & TBL >2xULN; ALT or AST >10xULN & TBL >2xULN
ALP & TBL	ALP >3xULN & TBL >2xULN ALP >5xULN & TBL >2xULN
ALT or AST & TBL & ALP	ALT or AST >3xULN & TBL >2xULN & ALP <2xULN (Hy's Law) Note: elevated ALP may suggest obstruction as a consequence of gall bladder or bile duct disease; ALP may also be increased in malignancy. FDA therefore terms Hy's Law cases as indicators of pure hepatocellular injury . This does not mean that cases of ALT or AST >3xULN & TBL >2xULN & ALP ≥2xULN may not result in severe DILI.

Notes: 1) In studies which enroll subjects with pre-existing liver disease, baseline LFT may be increased above ULN; in such a case it is meaningful to add the condition “and worse than baseline” to the abnormality criteria

For a combined criterion to be fulfilled, all conditions have to be fulfilled on the same visit. The criteria are not mutually exclusive, e.g. a subject with ALT = 6.42xULN is counted for ALT >3xULN and ALT >5x ULN.

Individual subject laboratory data listings will be provided for all subjects as well as for subjects with newly occurring or worsening CTCAE grades, or with newly occurring or worsening after baseline abnormalities in lipid parameters, or with newly occurring or worsening after baseline abnormalities in liver enzymes.

No box plots over time or other graphs will be presented for any of the laboratory parameters.

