14.4 Electrocardiogram (ECG)

The summary of ECG will only include on treatment data, which are defined as those ECG measurements after the first dose of study treatment and on or before last dose + 84 days.

The following quantitative variables will be summarized: ventricular rate, RR interval, PR interval, QRS duration, QT interval, and corrected QT interval (QTc). Both Bazett (QTcB) and Fridericia (QTcF) corrections will be presented for QTc.

QTc will only be summarized by computing the number and percentage of subjects (including 95% confidence intervals for pooled analyses, e.g. DMC or SCS) with:

- QTc > 500 msec
- QTc > 480 msec
- QTc > 450 msec
- QTc changes from baseline > 30 msec
- QTc changes from baseline > 60 msec
- PR > 250 msec

Subjects with notable abnormal ECG parameters as described above, after baseline will be summarized.

Summary statistics will be presented for ECG variables by visit and treatment dose in safety population.

Shift tables comparing baseline ECG interpretation (normal, abnormal, not available, total) with the worst on-study interpretation (normal, abnormal, not available, total) will be provided.

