 Group11: X-ray

Analysis Visit	Target Day	Analysis Visit Window	Group 1	Group 2	Group 3	Group 4	Group5	Group6	Group7	Group8	Group9	Group1 0	Group1 1	Group1 2	Group1 3	Group1 4	Group1 5
Group12: Immunology, [REDACTED] Group13: Weight Group14: Pregnancy test, hormones Group15: Vital signs																	
* The first administration of randomized study treatment (first dose) is defined as 1.																	

The following rules are used to determine the window for an applicable visit post baseline: “Lower limit” = “upper limit of prior applicable visit” + 1. “Upper limit” = “target day of current visit” + integer part of (“target day of next applicable visit” – “target day of current visit”)/2. Lower limit of the first applicable visit is always Day 2.

The mapping described above applies to all visits including optional site visits (not just scheduled visits). Optional site visits, repeat and/or unscheduled visits (which will be numbered in the database according to new NCDS standards) will be mapped for analysis purposes in the same way as scheduled visits. This leaves the possibility, then, for multiple measurements within an analysis window. The following conventions will be used to determine the appropriate measurement to be summarized in the event of multiple measurements within a visit window.

Table 17-2 Rules for flagging variables

Timing of measurement	Type of data	Rule
Baseline of core	All data	The last measurement made prior to administration of the first dose of study treatment in core– note this may include measurements taken on the day of randomization (e.g. lab). If a patient did not receive any dose of study treatment then the randomization date will be used.
Post-baseline efficacy	All data	The measurement closest to the target will be used. In the event two measurements are taken equally apart (e.g. 1 before target date and 1 after) the first one will be used.
Post-baseline safety	Summary visit information (e.g. lab, ECG, etc.)	The measurement closest to the target will be used. In the event two measurements are taken equally apart (e.g. 1 before target date and 1 after) the first one will be used.
Post-baseline safety	Notable abnormalities (e.g. lab)	The most extreme measurement in the window will be used. Note this means a patient can have a notably high and notably low measurement within a window.

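### Notable vital-sign, laboratory and ECG abnormalities are planned only as crude ever-notable percentages by dose received, and these are expected to run lower at 300 mg simply because 300 mg has fewer readings

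*SAP*

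**What the plan says.** SAP 14.3 sets the limits in Table 14-4 (systolic 140 mmHg or above, or below 90; diastolic 90 or above, or below 60; pulse above 100 or below 60) and says "The number and percentage of subjects with newly occurring notable vital signs will be presented". On-treatment data run to the last dose plus 84 days.

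In Table 14-1 (SAP 14.1) the column headed "Notables for (vitals/ ECG), lab criteria" contains crude incidence only, for the entire treatment period. The AE/SAE and risk columns also carry exposure-adjusted incidence, and the SMQ column carries only that. SAP 14.1 says that such rates are given "to adjust for differences in exposure".

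For notable abnormalities Table 17-2 says "The most extreme measurement in the window will be used". For liver criteria, SAP 14.2 says "For a combined criterion to be fulfilled, all conditions have to be fulfilled on the same visit", so one visit is enough. No repeat or confirmation is asked for.

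SAP 5.1 defines the safety columns as any 75 mg, any 150 mg, any 300 mg and any secukinumab. SAP 14 pools core and extension and says that subjects who change treatment "will be counted to both groups using the appropriate start and stop exposure date". Protocol 5.5.5 bars dose changes before Week 156.

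**The concern.** The SAP does not spell out a single-reading rule for vital signs and ECG. It follows from the words newly occurring and after baseline, and from taking the most extreme value. A percentage of that kind rises with the number of readings even if treatment does nothing. The dose columns differ in this by design: the lower doses accumulate readings from the core study onwards, while 300 mg can start only in the last two of the five years. The SAP recognises unequal exposure for adverse events but makes no allowance for it here.

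Vital signs and laboratory variables are named measures of the secondary safety objective (Protocol 2.2). A reader who compares the dose columns could take a lower 300 mg percentage as reassurance about the higher dose when it reflects fewer assessments.

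**Working it through.** **Plan's own figure.** The documents give no expected frequency of notable abnormalities. The only sizing figure, 460 to 520 eligible subjects, adds up (320 + 140 = 460; 360 + 160 = 520) but has no bearing here.

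**Vital-sign readings per subject.**
- Core windows visible in SAP 17.1, Group 15: Weeks 60, 68, 76, 84, 92, 100, 104 = 7. Earlier windows are not in the text, so this is a minimum.
- Protocol Table 6-1: Weeks 116, 128, 140, 156 = 4. Table 6-2: Weeks 168, 180, 192, 208 = 4. Table 6-3: Weeks 220, 232, 244, 260, 268 = 5. Total 13.
- Week 268 counts because the last dose is at Week 256 and 84 days is 12 weeks.
- One dose throughout: at least 7 + 13 = 20, of which 7 + 4 = 11 fall by Week 156.
- 300 mg from Week 156: at most 4 + 5 = 9, because the Week 156 reading precedes dosing. From Week 208: 5.

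The same count gives at least 19 against at most 9 for laboratory tests, and at least 7 against at most 4 for ECG.

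**Simplest null.** If each reading is notable with probability p, independently and equally at every dose, P(at least one in k) = 1 − (1 − p)^k. With p = 5%: 64% for k = 20, 37% for k = 9, 23% for k = 5.

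**Null with correlated readings.** Systolic reading = subject mean + visit noise, both normal, rounded to integers; subjects notable at baseline are excluded; no drug or dose effect. Means and SDs are assumptions, as the documents give none.

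| Assumption (mean, between SD, within SD) | 20 readings | 9 readings |
|---|---|---|
| Low (125, 10, 7) | 40% | 29% |
| Middle (128, 12, 9) | 63% | 48% |
| High (130, 13, 10) | 73% | 57 to 58% |

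A still lower setting (122, 9, 6) gives 22% against 15%. The direction does not change; the size does.

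**Rare criteria.** With an assumed p = 0.2% and independent readings: laboratory 1 − 0.998^19 = 3.7% against 1 − 0.998^9 = 1.8%; ECG 1 − 0.998^7 = 1.4% against 1 − 0.998^4 = 0.8%. The laboratory ratio is about two, but the absolute gap is small.

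**Would an exposure-adjusted rate cure it?** SAP 17.3.4.1 uses D/T, with T the summed time to first event or end of observation. Under the middle systolic null, with the long-stay clock started at Week 52 because earlier visits are not shown, the rates per 100 subject-years are about 28 (20 readings), 32 (300 mg from Week 156) and 40 (300 mg from Week 208). Under the low assumptions they are about 13, 16 and 21. Susceptible subjects are flagged at their first visits, so the first-event rate falls with follow-up and the shorter column looks worse.

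**The case against.** The strongest reply is that these counts are one descriptive display among several. The SAP plans vital-sign change from baseline by visit and dose (14.3), laboratory values, changes and low/normal/high shifts by visit and dose (14.2), and ECG statistics by visit and dose (14.4). None of these grows with the number of visits. This stands: a reader might infer that the plan cannot show whether a higher dose shifts blood pressure or laboratory values, and that would be wrong. But by-visit means do not give the proportion notable, and by-visit shifts use the normal range rather than the notable multiples. For QTc the backstop is weaker, since SAP 14.4 says "QTc will only be summarized by computing the number and percentage of subjects".

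Second, completers on one dose are not the columns. The safety set includes core drop-outs (606 subjects in core, 460 in the extension), and an escalator's earlier time stays in the lower-dose column. An escalator who left 150 mg at Week 156 contributes 11 visible readings there; under the middle systolic null that gives 52%, against 48% for 9 readings on 300 mg. Escalators are also selected as not fully controlled. This stands, and it shrinks the gap by an amount the documents do not allow one to compute.

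Third, the SAP says "No formal hypotheses are planned for this study", and 14.3 plans no interval for notable vital signs. A reader might go on to put a probability on 300 mg being falsely favoured. The documents do not support one: they give no column sizes, escalation dates or per-reading rates, and switchers appear in more than one column.

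**Conclusion.** The point holds as a reporting weakness that should be fixed. Crude ever-notable percentages by dose received depend on the number of assessments, and the schedule gives at least 20 vital-sign readings against at most 9. With equal risk per reading, the 300 mg percentage is expected to be lower. For systolic pressure the completer-level gap is about 11 to 16 percentage points under the three tabulated assumptions and smaller in the actual columns.

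Two stronger readings are tempting. One is that the rule flags most long-stay subjects: for systolic pressure alone that happens under the middle and high assumptions but not the low ones, and it does not extend to rare laboratory or QTc criteria. The other is that 300 mg will look safest: that is the expected direction under no effect, not a certainty, given selection and the mix within columns. For ECG even the direction is uncertain, because only 3 readings are visible by Week 156 against up to 4 on 300 mg.

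**What to change.** 1. In SAP 14.3 and the last column of Table 14-1, add the number and percentage of subjects notable at each scheduled visit, by dose at the time of the reading, among subjects not notable at core baseline. Do the same for laboratory and ECG criteria that the by-visit shift tables do not already cover. Under no effect this percentage does not grow with the number of visits. It does not remove the selection of escalators.
2. Footnote the crude ever-notable, maximum-change and worst-value tables: they depend on the number of assessments and should not be compared between dose columns.
3. State whether newly occurring, for a subject on a second dose, is judged against core baseline or the value before escalation. The SAP leaves this open.
4. If an exposure-adjusted rate by SAP 17.3.4.1 is added, label it supportive and say that first-event rates are higher with shorter follow-up, so it can bias against 300 mg.

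The cost is SAP wording and a few extra tables from data already collected, with no new visits or patients. The downside is somewhat more safety output.
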